4.2.2.2 Restrictions on diet and life style

No specific restrictions on diet or life style of the patients are required.

Emollients will be provided by the sponsor for the patient's use during the trial. However, emollients must not be used on all visit days prior to the PPP assessments. Further details will be provided in ISF

4.2.2.3 Contraception requirements

Women of childbearing potential (for the definition of WOCBP, please refer to [Section 3.3.3](#)) must use highly effective methods of birth control per ICH M3 (R2) that result in a low failure rate of less than 1% per year when used consistently and correctly during the trial, and for a period of at least 16 weeks after the last study drug administration. A double barrier method of contraception is not required. A list of contraception methods meeting these criteria is also provided in the patient information.

Female Patients:

Acceptable methods of birth control for this trial are:

- Combined (estrogen and progestogen containing) hormonal birth control that prevents ovulation (oral, intravaginal, transdermal)
- Progestogen-only hormonal birth control that prevents ovulation (oral, injectable, implantable)
- Intrauterine device (IUD) or intrauterine hormone-releasing system (IUS)
- Bilateral tubal occlusion
- Vasectomised sexual partner with documented absence of sperm

Or

Patients must abstain from male-female sex. This is defined as being in line with the preferred and usual lifestyle of the patient. Periodic abstinence e.g. calendar, ovulation, symptothermal, post-ovulation methods; declaration of abstinence for the duration of exposure to study drug; and withdrawal are not acceptable.

Male Patients:

Contraception of male trial participants and female partners of male trial participants are not required.

4.3 TREATMENT COMPLIANCE

Treatment compliance will be calculated as shown in the formula below. Compliance will be verified by the Clinical Research Associate (CRA) authorised by the sponsor.

$$\text{Treatment compliance (\%)} = \frac{\text{Number of actual injections} \times 100}{\text{Number of per protocol planned injections}}$$

The measured plasma concentrations will provide additional information about compliance.

5. ASSESSMENTS

5.1 ASSESSMENT OF EFFICACY

5.1.1 Palmoplantar Pustulosis Area and Severity Index (PPP ASI)

The Palmoplantar Pustulosis Area and Severity Index (PPP ASI) is an investigator assessment of the extent and severity of pustular and plaque lesions on the palms and soles presenting in PPP patients. The adaptation from [REDACTED] an established measure of severity and area of psoriatic lesions in patients with psoriasis, by Bhushan et.al [R16-5334] will be used in this trial.

This tool provides a numeric scoring for patients overall PPP disease state, ranging from 0 to 72. It is a linear combination of the percent of surface area of skin that is affected on the palms and soles of the body and the severity of erythema, pustules, and scaling (desquamation).

The PPP ASI will be measured at the timepoints noted in the [Flow Chart](#). The PPP ASI is provided in [Appendix 10.1.1](#).

5.1.2 Palmoplantar Pustulosis Physician Global Assessment (PPP PGA)

The Palmoplantar Pustulosis Physician Global Assessment (PPP PGA) relies on clinical assessment of the patient's skin presentation on the palms and soles. The investigator scores the individual components (erythema, pustules and scaling/crusting) from 0 to 4 as clear, almost clear, mild, moderate or severe.

[figure not shown]
PPP PGA is using severity scores for erythema, pustules, and scaling. The PPP PGA will be analyzed as PPP PGA total score including erythema, pustules and scaling, and as PPP PGA pustules score for pustules only. Further details and practical guidance will be available in the ISF.

[figure not shown]
The PPP PGA will be measured at the timepoints noted in the Flow Chart. The PPP PGA is provided in [Appendix 10.1.2](#).

5.1.3 Pain VAS (Visual Analogue Scale)

The pain VAS is a unidimensional measure of pain intensity [R18-1989]. It is a continuous scale comprised of a horizontal or vertical line, usually 10 centimeters (100 mm) in length, anchored by word descriptors at each end ("no pain", "very severe pain"). The pain VAS is self-completed by the patient. The patient is asked to place a vertical (|) mark on the horizontal line to indicate the severity of the pain. Using a ruler, the score is determined by measuring the distance (mm) on the 10-cm line between the "no pain" anchor and the patient's mark, providing a range of scores from 0–100. A higher score indicates greater pain intensity.

Pain VAS will be measured at the timepoints noted in the Flow Chart. The Pain VAS instrument to assess is provided in [Appendix 10.1.3](#). Of note, there will be two pain VAS questionnaires, one specifically asking for pain on palms and/or soles (PPP Pain VAS) and one for muscular and joint pain.

5.1.10 Palmoplantar Pustulosis Severity Index (PPP SI)

The Palmoplantar Pustulosis Severity Index (PPP SI) is based on the severity score of individual components (erythema, pustules, and scaling/desquamation) of PPP ASI assessments. The most severe skin lesion location is identified by the investigator at baseline and assessed at all subsequent visits.

The PPP SI will be calculated by summing up the individual components of PPP ASI assessment (range 0-12) at each visit for the identified location.

PPP SI will be measured at the timepoints noted in the Flow Chart. Details are provided in [Appendix 10.1.10](#).

5.2 ASSESSMENT OF SAFETY

Safety will be assessed descriptively based on:

- Adverse events (including drug-related AEs and AEs leading to discontinuation)
- Adverse events of special interest (AESIs)
- Serious adverse events (SAEs)
- Intensity of adverse events will be assessed by Rheumatology Common Toxicity Criteria (RCTC) version 2.0 (refer to [Appendix 10.3](#) and ISF for details)
- Safety laboratory tests
- Physical examination
- Vital signs (blood pressure, pulse rate, body temperature, respiratory rate)
- 12-lead Electrocardiogram (ECG)
- Local tolerability
- Immunogenicity (ADA/Nab)

5.2.1 Physical examination

A complete physical examination will be performed at the time points specified in the Flow Chart. It includes at a minimum general appearance, neck, lungs, cardiovascular system, abdomen, extremities, and skin.

Targeted physical examination will include vital sign assessment and evaluation of organ systems associated with AE(s) symptoms or laboratory abnormalities.

Measurement of height and body weight will be performed at the time points specified in the [Flow Chart](#).

The results must be included in the source documents available at the site.

5.2.2 Vital signs

Vital signs will be evaluated at the time points specified in the Flow Chart, prior to blood sampling. Measurements of vital signs should be assessed at screening. At dosing visits, vital signs evaluations will be performed pre-dose and additional evaluations will be taken at 10 minutes post-dose and 1 hour after the end of the study drug administration.

This includes systolic and diastolic blood pressure and pulse rate (electronically or by palpation count for 1 minute) in a seated position after 5 minutes of rest, and additionally temperature and respiratory rate. The results must be included in the source documents available at the site.

5.2.3 Safety laboratory parameters

Safety laboratory parameters to be assessed are listed in Table 5.2.3: 1. For the sampling timepoints please see the Flow Chart.

All analyses will be performed by a central laboratory, the respective reference ranges will be provided in the ISF.

Patients do not have to be fasted for the blood sampling for the safety laboratory.

Instructions regarding blood and urine sample collection, sample handling/ processing and sample shipping are provided in the laboratory manual in the ISF.

The central laboratory will send reports to the investigator. It is the responsibility of the investigator to evaluate the laboratory reports. Clinically relevant abnormal findings as judged by the investigator will be reported as adverse events (please refer to [Section 5.2.6](#)).

In case the criteria for hepatic injury are fulfilled, a number of additional measures will be performed (please see [Section 5.2.6.1](#) and the DILI Checklist provided in the ISF). The amount of blood taken from the patient concerned will be increased due to this additional sampling.

The central laboratory will transfer the results of the analysis to the sponsor.

Table 5.2.3: 1 Safety laboratory tests

Category	Test name
Haematology	Haematocrit (Hct) Haemoglobin (Hb) Glycosylated Hbc (HbA1c) (only at screening) Red Blood Cell Count Reticulocyte Count White Blood Cells / Leukocytes Platelet Count / Thrombocytes

Table 5.2.3: 1 (cont.) Safety laboratory tests

Category	Test name
Diff. Automatic	Neutrophils (relative and absolute) Eosinophils (relative and absolute) Basophils (relative and absolute) Monocytes (relative and absolute) Lymphocytes (relative and absolute)
Diff. Manual (if Diff Automatic is abnormal)	Neutrophils, bands (Stabs) Neutrophils, polymorphonuclear (PMN) Eosinophils Basophils Monocytes Lymphocytes
Coagulation	Partial Thromboplastin Time (aPTT) Prothrombin time (INR) Fibrinogen
Enzymes	AST (GOT) ALT (GPT) Alkaline Phosphatase (AP) Creatine Kinase (CK) CK-MB, only if CK is elevated Gamma-Glutamyl Transferase (GGT/ γ -GT) Lactic Dehydrogenase (LDH) Amylase Lipase Serum Tryptase ¹
Electrolytes	Calcium Sodium Potassium Chloride Bicarbonate
Substrates	Glucose BUN (blood urea nitrogen) Uric acid Creatinine eGFR (estimated by CKD-EPI formula) (only at screening) Bilirubin Total Bilirubin Direct (if total is elevated) Bilirubin Indirect (if total is elevated) Troponin (Reflex, in case of elevated CK) Protein, Total Albumin C-Reactive Protein (CRP) (high sensitivity) Cholesterol, total Triglycerides LDL-Cholesterol HDL-Cholesterol
Specific gamma-globulin quantification	IgE ³
Urine Pregnancy test ² (only for female patients of childbearing potential). At the drug administration visits, the test will be performed prior to the administration of study drug	Human Chorionic Gonadotropin in urine
Serum Pregnancy test ² (only for female patients of childbearing potential)	Human Serum Chorionic Gonadotropin

Table 5.2.3: 1 (cont.) Safety laboratory tests

Category	Test name
Hormones (only at screening)	TSH (free T3 and free T4 in case of abnormal TSH result)
Urinalysis	Urine Nitrite Urine Protein Urine Glucose Urine Ketone Urobilinogen Urine Bilirubin Urine RBC / Erythrocytes Urine WBC / Leukocytes Urine pH Urine Creatinine
Urine-Sediment (microscopic examination, only if urine analysis abnormal)	Urine Sediment Bacteria Urine Cast in Sediment Urine Squamous Epithelial Cells Urine Sed. Crys., Unspecified Urine Sediment RBC / Erythrocytes Urine Sediment WBC / Leukocytes
Urine (only at screening)	Albumin (quantitative)
Infections testing	Hepatitis B Surface Antigen (qualitative), Hepatitis B core Antibody HBV-DNA (quantitative) at screening (Visit 1) and EOT Visit ⁴ Hepatitis C Antibodies (qualitative), HIV-1, and HIV-2 Antibody (qualitative), QuantiFERON®-TB ^{5,6}

¹ Performed only at the randomisation visit (Visit 2).

² Urine and serum pregnancy testing will be performed as indicated in the [Flow Chart](#).

³ IgE will be taken in case of systemic hypersensitivity reaction together with ADA (anti-drug antibodies) sample.

⁴ A HBV-DNA should be conducted if Hepatitis B core Antibody is positive and Hepatitis B Surface Antigen is negative. These evaluations should be conducted at screening and at the EOT Visit.

⁵ If the 1st QuantiFERON®-TB test result is indeterminate, a retest should be performed

⁶ In patients with a negative QuantiFERON®-TB test, the test should be repeated at EOT visit.

5.2.4 Electrocardiogram

The 12-lead ECGs must be administered by a qualified technologist and results will be recorded as scheduled in the Flow Chart. The investigator or a designee will evaluate whether the ECG is normal or abnormal and assess clinical relevance. ECGs may be repeated for quality reasons and a repeated recording used for analysis. Additional ECGs may be recorded for safety reasons. Dated and signed printouts of ECG with findings should be documented in patient's medical record.

Clinically relevant abnormal findings will be reported either as baseline condition (if identified at the screening visit) or otherwise as AEs and will be followed up and/or treated as medically appropriate.

5.2.5 Other safety parameters

All cases of malignancies that are detected during the trial will be reported as SAEs. Patients with a history of malignancy (except for specific cancers) will be excluded from this trial per the exclusion criteria ([Section 3.3.3](#)).

5.2.6 Assessment of adverse events

5.2.6.1 Definitions of AEs

5.2.6.1.1 Adverse event

An AE is defined as any untoward medical occurrence in a patient or clinical investigation subject administered a medicinal product and which does not necessarily have to have a causal relationship with this treatment.

An AE can therefore be any unfavourable and unintended sign (including an abnormal laboratory finding), symptom, or disease temporally associated with the use of a medicinal product, whether or not considered related to the medicinal product.

The following should also be recorded as an AE in the CRF and BI SAE form (if applicable):

- Worsening of the underlying disease or of other pre-existing conditions
- Changes in vital signs, ECG, physical examination and laboratory test results, if they are judged clinically relevant by the investigator.

If such abnormalities already exist prior to trial inclusion, they will be considered as baseline conditions and should be collected in the eCRF only.

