2.1.3 Secondary endpoint(s)

Secondary endpoints are defined as described below. Note that for the secondary endpoints, any data collected after use of any rescue therapy or after 6 weeks following discontinuation of treatment (to allow for incorporation of the continuing maximum treatment effect period) are censored for the purpose of the primary estimand.

- Change from baseline in PPP Pain Visual Analog Scale (VAS) score at Week 4 and 16
- PPP SI change from baseline at Week 16
- PPP ASI₅₀ at Week 16
- PPP ASI₇₅ at Week 16
- PPP PGA clear/almost clear at Week 16
- PPP PGA pustules clear/almost clear at Week 16
- Percent change in PPP ASI from baseline at Week 52

- The occurrence of Treatment Emergent Adverse Events (TEAEs)

[figure not shown]

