3.3.4.1 Discontinuation of trial treatment

An individual patient will discontinue trial treatment if:

- The patient wants to discontinue trial treatment, without the need to justify the decision.
- The patient has repeatedly shown to be non-compliant with important trial procedures and, in the opinion of both, the investigator and sponsor representative, is not willing or able to adhere to the trial requirements in the future.
- The patient needs to take rescue therapy, see Section 4.2.2.1.
- The patient can no longer receive trial treatment for medical reasons (such as surgery, adverse events, other diseases, or pregnancy).

Even if the trial treatment is discontinued, the patient remains in the trial and, given his/her agreement, ideally should follow the visits and procedures outlined in the [Flow Chart](#), including the EOT and EOS visits.

If the patient is not willing to follow the whole visit schedule, at least the EOT should be conducted either immediately or as soon as possible followed by the EOS visit 16 weeks after the EOT visit.

The trial treatment discontinuation criteria apply from Week 24 onwards and require assessment and confirmation at 2 consecutive visits (discontinuation itself will apply at the second visit in the sequence)

- No reduction in pustulation severity compared to baseline

AND

- No reduction in PPP ASI of ≥ 5 points compared to baseline

A patient who meets the trial treatment discontinuation criteria may be discontinued from the trial treatment and administered rescue therapy as judged by the investigator.

The earliest trial treatment discontinuation timepoint according to this rule is at Week 28.

For individual stopping rules related to specific adverse events, please see [Section 4.2.1](#) (Other treatments and emergency procedures).

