In the event a patient with prior use of biologic treatment, systemic steroids or immunomodulating treatments is enrolled, past medical records are required to document when these treatments were stopped. All concomitant or rescue therapies will be recorded (including time of intake and dose on study days) on the appropriate pages of the CRF.

Restrictions regarding concomitant treatment during the trial

Topical treatment

Topical treatment for PPP is not allowed throughout the study. Topical treatment for other conditions is not restricted, however, the patient should avoid applying it with bare hands (e.g. use gloves) when the topical treatment is applied on affected body areas.

Topical corticosteroids

Topical corticosteroids for the treatment of PPP are not allowed during the trial unless they are needed as rescue therapy. Topical corticosteroids for body area other than palms and soles are allowed. The dose and mode of administration should be kept unchanged, if possible. The patient should avoid applying it with bare hands (e.g. use gloves).

Systemic immunomodulating treatments

Systemic corticosteroids and other immunomodulating agents (such as methotrexate, fumaric acid acitretin, ciclosporin, apremilast) for the treatment of PPP are not allowed unless they are needed as rescue therapy.

Biologic treatment

Biologic treatment is not allowed throughout the study, unless it is needed as rescue therapy.

Non-steroidal anti-inflammatory drugs (NSAIDs)

The use of NSAIDs is allowed, however it is recommended that a stable dose is maintained and the drug is not changed throughout the study up to at least the primary endpoint at Week 16.

Rescue therapy for the treatment of worsening of PPP

Rescue therapy is defined as both the use of medication such as topical corticosteroids or other topical treatment applied on the palms and/or soles, systemic immunomodulating treatments or biologics and therapy such as tonsillectomy, for the treatment of worsening of PPP.

The use of the rescue therapy leads to the discontinuation of the trial treatment, but the patient should remain in the trial observation.

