7.8.1 Adverse events

AEs will be coded with the most recent version of MedDRA.

The analyses of AEs will be descriptive in nature. All analyses of AEs will be based on the number of patients with AEs and not on the number of AEs. System organ classes (if applicable) will be sorted according to the standard sort order specified by the EMA, preferred terms (if applicable) will be sorted by total frequency (within system organ class) across all treatment arms, or, if a total column across all arms is not foreseen in the table, by total frequency (within system organ class) across the BI arms.

For details on summarization of AE data, please refer to "Handling and summarization of adverse event data for clinical trial reports and integrated summaries" (7) and "Handling of missing and incomplete AE dates" (4).

The analysis of AEs will be based on the concept of treatment emergent AEs. Since only the start date of an AE is collected (without start time), any AE occurrence on the same day as the first Spesolimab administration will be assigned to the on-treatment phase.

An overall summary of AEs will be presented by treatment. This overall summary will include summary statistics for the class of other significant AEs (sponsor definition based on ICH E3) and for the class of AESIs.

Based on the specification provided in ICH E3 (9), the sponsor has defined AEs which are to be classified as 'other significant'. For the current trial, these will include those non-serious AEs which were reported with 'action taken = Drug withdrawn' or 'action taken = Dose reduced'.

The following is considered an AESI in this trial:

Systemic hypersensitivity reactions including anaphylactic reaction

Severe infections (according to RCTC grading in CTP Appendix 10.2)

Opportunistic and mycobacterium tuberculosis infections

Hepatic injury

The investigator had to classify on the eCRF whether an observed AE was an AESI or not.

In addition, user defined adverse event concepts (UDAEC) identified through specific search criteria will be reported separately (see [Table 7.8.1: 1](#)).

Table 7.8.1: 1 Project MEDDRA search criteria for User Defined Adverse Events Concepts

User Defined AE Concepts	Categories
Infusion/Systemic hypersensitivity reactions including anaphylactic reactions	Narrow SMQ “Anaphylactic reaction” Narrow SMQ “Angioedema” Narrow SMQ “Hypersensitivity”
Opportunistic infections	Narrow SMQ “Opportunistic infections”:

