Tuberculosis infections	BICMQ Narrow sub-search 8.2 “Tuberculosis related terms”
Malignant tumours	Narrow Sub-SMQ “Malignant tumours” Narrow Sub-SMQ “Haematological malignant tumours” Narrow Sub-SMQ “Non-Haematological malignant tumours”
Malignant skin tumours	Broad Sub-SMQ “Skin malignant tumours”
Skin melanomas	HLT Skin melanomas (excl. Ocular)
Non-melanoma skin cancer (NMSC)	Broad sub-BICMQ “Skin Malignancies excluding melanomas”
Malignancies excluding NMSC	Sub-SMQ “Malignant tumours” excluding broad sub-BICMQ “Skin Malignancies excluding melanomas”
3-point MACE	BICMQ 3-MACE with subsearch 1.1 narrow and subsearch 1.2 narrow *
Torsades de pointes	Broad SMQ “Torsades de pointes/QT prolongation”
Severe infections (according to RCTC grading)	SOC Infections and infestations of at least severe RCTC grade, by HLGT

* this is achieved by retrieving all cases found either by running subsearch 1 in narrow scope (BICMQ search ID 32019093) or subsearch 2 (BICMQ search ID 32019094)

The frequency of patients with AEs will be summarised by treatment, primary system organ class and preferred term. AEs which were considered by the investigator to be drug related will be summarised separately. Separate tables will also be provided for patients with SAEs, patients with AESIs, patients with AE leading to discontinuation of the trial medication, and patients with other significant AEs (as described previously). AEs will also be summarized by maximum intensity.

For disclosure of AE data on ClinicalTrials.gov, the frequency of patients with non-serious AEs occurring with an incidence of greater than 5 % (in preferred terms) will be summarised by treatment, primary system organ class and preferred term. The frequency of patients with SAEs and drug related SAEs will also be summarised respectively.

For disclosure of AE data in the EudraCT register, the frequency of non-serious AEs with an incidence of greater than 5 % (in preferred terms) and the frequency of SAEs will be summarised.

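### Worsening of PPP is recorded as an adverse event, so the any-TEAE row mixes lack of efficacy with other harms and can dilute an excess of other AEs on active drug

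*Protocol*

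**What the plan says.** **Recording.** Protocol 5.2.6.1.1 lists, among the things to be recorded as an AE, "Worsening of the underlying disease or of other pre-existing conditions". The visible text makes no exception for PPP.

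**Endpoint and window.** Occurrence of TEAEs is a secondary endpoint in Protocol 2.1.3 and again in SAP 5.2.2. Under Protocol 7.2.5 an AE is treatment-emergent if it starts between first dose and 16 weeks after the last dose. There is no carve-out for the disease under study.

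**Counting.** SAP 7.8.1 states: "All analyses of AEs will be based on the number of patients with AEs and not on the number of AEs". It plans an overall summary, tables by system organ class and preferred term, and separate tables that include "patients with AE leading to discontinuation of the trial medication" and other significant AEs. The last group is non-serious AEs whose recorded action was drug withdrawal or dose reduction. None of these is planned without PPP worsening.

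**Rescue.** Protocol 4.2.2.1 defines rescue as treatment for worsening of PPP and adds: "The use of the rescue therapy leads to the discontinuation of the trial treatment, but the patient should remain in the trial observation". Protocol 3.3.4.1 gives "The patient needs to take rescue therapy, see Section 4.2.2.1" as its own reason for stopping. Medical reasons, with adverse events among the examples, are a separate item. No visible rule says which applies when both do.

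**Use.** Protocol 2.1.1 says the target dose takes account of safety, and SAP 7.4 says safety is considered in choosing the Phase 3 dose. Safety analysis is descriptive, without hypothesis tests (Protocol 7.2.5, SAP 7.8).

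**The concern.** A patient-level count of any TEAE is a yes/no that is satisfied by a PPP flare as readily as by an infection or an injection reaction. Section 1.4.2 of the protocol accepts that patients on placebo may get worse. If the drug is effective, worsening will be more frequent on placebo, so the any-TEAE proportion rises there for reasons unrelated to tolerability. The contrast then moves in favour of active drug, and an excess of other AEs can look smaller than it is or disappear.

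The direction follows from the design and does not depend on chance. The contrast concerned is mainly active against placebo up to Week 16, because SAP 6.1 relabels Arm 5 as receiving spesolimab afterwards. What is at stake is a clear reading of one declared secondary endpoint and, where site recording allows it, of two further summary rows that help to describe tolerability.

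**Working it through.** The documents state no rate of AEs, PPP worsening or rescue, so there is no figure of the plan to reproduce. Every rate below is an assumption, chosen to show direction and range. The arm sizes are from the protocol synopsis: 40 placebo and 40+20+20+20 = 100 active.

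**1. Any TEAE.** Let *a* be the proportion with a TEAE other than PPP worsening and *w* the proportion with PPP worsening, taken as independent. Then P(any TEAE) = 1 − (1 − a)(1 − w). Assume a = 50% on placebo and 60% on active, a true excess of +10 points.

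| w placebo / active | Any TEAE placebo | Any TEAE active | Apparent excess |
|---|---|---|---|
| 5% / 5% | 52.5% | 62.0% | +9.5 |
| 10% / 5% | 55.0% | 62.0% | +7 |
| 20% / 20% | 60.0% | 68.0% | +8 |
| 20% / 10% | 60.0% | 64.0% | +4 |
| 20% / 5% | 60.0% | 62.0% | +2 |
| 30% / 5% | 65.0% | 62.0% | −3 |

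For the fifth row: 1 − 0.50 × 0.80 = 0.60 and 1 − 0.40 × 0.95 = 0.62. With 5% worsening on active, the excess vanishes when placebo worsening reaches 1 − (0.40 × 0.95)/0.50 = 24%. Starting from 60% vs 70%, the break-even is 1 − (0.30 × 0.95)/0.40 = 28.7%. Equal worsening in both groups costs little at low rates. The loss comes from the difference in worsening between groups.

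**2. Can the preferred-term table repair this?** In the 20% / 5% case, placebo shows 40 × 0.60 = 24 patients with any TEAE and 40 × 0.20 = 8 with the PPP term. Between 0 and 8 of those 24 have PPP worsening only, so from these two counts the number with any other TEAE lies between 24 − 8 = 16 and 24. Counts for other terms can raise the lower bound but do not in general fix the number, because terms overlap within patients. Patient-level listings would fix it.

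**3. AEs leading to discontinuation.** Let *f* be the share of worsening-driven stops that sites record as drug withdrawal on the PPP AE. Assume stops for other AEs in 2% of placebo and 6% of active patients (true excess +4 points), and worsening-driven stops in 10% and 2%. Replace *w* by *f × w* in the same formula.

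| f | Placebo | Active | Apparent excess |
|---|---|---|---|
| 0 | 2.0% | 6.0% | +4.0 |
| 0.5 | 6.9% | 6.9% | 0.0 |
| 1 | 11.8% | 7.9% | −3.9 |

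For f = 1: 1 − 0.98 × 0.90 = 0.118 and 1 − 0.94 × 0.98 = 0.0788. The result runs from no effect to a reversed sign, depending only on a recording habit that the documents do not fix. The row for other significant AEs depends on *f* in the same way.

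**The case against.** **Rescue is a separate reason for stopping.** A reader might infer that every rescued patient enters the AE-discontinuation and other-significant tables. The documents do not support that. Protocol 3.3.4.1 lists rescue and adverse events apart, and SAP 7 tabulates discontinuation by reason. With f = 0 nothing happens to those rows. This objection stands, and it limits the firm part of the point to the any-TEAE row.

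**The size is assumed, and chance is large.** For 50% vs 60% with 40 and 100 patients the standard error is √(0.50 × 0.50/40 + 0.60 × 0.40/100) = 0.093, about 9 points. The 8-point shift in the 20% / 5% case is of that order. In addition, the lack-of-response rule in Protocol 3.3.4.1 cannot stop treatment before Week 28, so it adds nothing to the placebo contrast up to Week 16. Both remarks stand. They make the size uncertain but do not remove the direction.

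**Much is shown elsewhere.** SAP 7.8.1 also plans drug-related AEs, SAEs, AESIs, user-defined concepts and AEs by maximum intensity. The AESI and concept categories are largely free of PPP worsening. Listings cover all patients, and rescue use is summarised separately in SAP 7.6.3, which is not in the public text. This is real mitigation, but in the visible text it does not supply a patient count of TEAEs other than PPP worsening.

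**Nothing is tested.** Safety is descriptive and no stated rule uses the any-TEAE row, so no error rate is affected. This stands.

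**Excluding worsening can itself mislead.** The protocol excludes patients with anti-TNF-induced PPP-like disease, which acknowledges that a biologic can provoke such lesions. Making a version without PPP terms the main comparison could hide drug-provoked worsening. This stands and shapes the fix.

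**Conclusion.** The point holds for the any-TEAE row. PPP worsening is recorded as an AE, the count is per patient, and no visible summary separates the two. An effective drug therefore shifts that row in its own favour, mainly against placebo up to Week 16. For AE discontinuations and other significant AEs the effect is conditional on how sites record the action taken when rescue is the trigger.

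The size is unknown. In the any-TEAE table above, an assumed 10-point excess shows as anything from +9.5 to −3 points. This rests on the assumed rates and on independence between PPP worsening and other AEs.

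Two stronger readings should be resisted. One is that the relation between dose and AEs would be inverted. Protocol 4.1.2 describes the lowest regimen as subtherapeutic, so a gradient in worsening between active arms is conceivable, but the documents give no rates by arm and nothing here computes such an inversion. The other is that recording worsening as an AE is a mistake. It is not, and collection should stay as it is.

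This is a minor weakness of presentation, worth correcting because it is directional and cheap to remove.

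**What to change.** In SAP 7.8.1, before the Week 16 unblinding:

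- List the preferred terms that denote worsening of PPP.
- Keep the all-event tables as the main display.
- Add supplementary rows, excluding those terms, for any TEAE, AEs leading to discontinuation and other significant AEs.
- Show PPP-worsening AEs separately by arm, so that drug-provoked worsening stays visible.

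The cost is a short term list and a few extra rows. AE collection and reporting do not change and no new data are needed.
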